#### 2.3.3 Exclusion criteria:

(1) A history of infection or other acute disease within one month prior to enrollment.

(2) People who are in a state of stress.

(3) Other unstable chronic diseases;

(4) A history of acute and chronic gastrointestinal diseases, including acute gastroenteritis, functional gastrointestinal diseases, inflammatory bowel disease, celiac disease, and other chronic gastrointestinal diseases.

(5) Individuals who have received systemic antibiotics, immunosuppressants, chemotherapy, or chronic treatment with proton pump inhibitors within the past three months will be excluded from participation.

(6) Pregnant or lactating women.

(7) Individuals who have participated in other drug clinical trials within the past three months.

(8) Individuals who suffer from mental illness, intellectual disability, confusion, or other conditions that may interfere with their ability to cooperate with the completion of relevant information collection will also be excluded.

In order to ensure the rigor and reliability of the study, subjects who met one or more of the aforementioned criteria were excluded.

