## 2 Methods

### 2.1 Trial overview, ethical consideration, and patient recruitment

This study is an ongoing, single-center, cross-sectional observational clinical trial. The subjects were selected for observation and subsequent analysis for key biomarkers such as blood glucose, Urine Albumin-to-Creatinine Ratio(UACR), and renal function. Blood, urine, feces, and moss on the tongue samples were collected from the subjects and stored for subsequent analysis. The study protocol was approved by the Ethics Committee of the First Affiliated Hospital of Hunan University of Traditional Chinese Medicine in accordance with the relevant ethical standards. The study is currently being conducted at the First Affiliated Hospital of Hunan University of Traditional Chinese Medicine and involves four groups of participants: type 2 diabetic kidney disease (DKD), type 2 diabetes mellitus (T2DM), chronic kidney disease (CKD), and healthy human. Subjects will be recruited from inpatients or outpatients of the Department of Endocrinology and the Department of Nephrology of the First Affiliated Hospital of Hunan University of Traditional Chinese Medicine. Additionally, healthy human subjects will be recruited from the general public through printed advertisements, invitations, etc. The total number of individuals proposed to be recruited in the four groups is 720.

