### 2.2 Study outcomes

**Primary outcome:** By employing a combination of microbiomic and metabolomic technologies, we conducted a comprehensive analysis of the intestinal flora and serum metabolic profiles associated with DKD. This approach enabled us to identify potential enterogenous disease markers of DKD and to investigate the metabolic profiles that may be linked to disease progression.

**Secondary outcome:** The objective of this study is to analyze the interaction between intestinal flora and intestinal-derived metabolites in the disease process of DKD. Additionally, the aim is to provide new disease diagnostic strategies and progression risk assessment indicators for diabetic nephropathy, which can be applied to early identification, precise diagnosis, and prognosis of the disease.

**Exploratory outcomes :** In accordance with the test results, each group will select four to six remaining fecal samples as the donor source for allogeneic fecal bacteria transplantation. Subsequently, the correlation between intestinal flora and enteric metabolites in diabetic nephropathy will be investigated through the method of human-mouse allogeneic flora transplantation.

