### 2.4 Study procedures

#### 2.4.1 Questionnaire to collect information

(1) General items: name, gender, age, BMI, education level, labor intensity, dietary preferences, etc;

(2) TCM symptoms, tongue and pulse;

(3) Clinical information: disease duration, other complications (e.g., diabetic peripheral neuropathy, diabetic retinopathy, diabetic cardiomyopathy, etc.), concomitant diseases (hypertension, coronary artery disease, hyperlipidemia, cerebrovascular disease, and hyperuricemia, etc.), past medical history, history of smoking, alcohol, family history, and history of drug use.

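### The drug exclusion does not reach gut-acting antibiotics, probiotics or a non-chronic PPI course at sampling, and the analysis plan does not adjust for them

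*Combined protocol and SAP*

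**What the plan says.** - **Drug exclusion.** Section 2.3.3, criterion (5), rules out anyone who has received "systemic antibiotics, immunosuppressants, chemotherapy, or chronic treatment with proton pump inhibitors within the past three months". The antibiotic term carries the qualifier systemic and the PPI term the qualifier chronic; neither is defined. Probiotics are not named here or elsewhere.
- **Scope.** The list closes by saying that "subjects who met one or more of the aforementioned criteria were excluded", so it applies to all four groups.
- **Neighbouring exclusions.** Criterion (1) is "A history of infection or other acute disease within one month prior to enrollment". Criterion (4) begins "A history of acute and chronic gastrointestinal diseases, including acute gastroenteritis, functional gastrointestinal diseases, inflammatory bowel disease".
- **Drug history.** The questionnaire in section 2.4.1 ends with "family history, and history of drug use". It asks for no drug class, date or look-back period.
- **Recruitment.** Section 2.1 says of the patients: "Subjects will be recruited from inpatients or outpatients of the Department of Endocrinology and the Department of Nephrology". By contrast, "healthy human subjects will be recruited from the general public through printed advertisements, invitations, etc".
- **Use of the stool data.** The primary outcome in section 2.2 is an analysis of the "intestinal flora and serum metabolic profiles associated with DKD". The exploratory outcome takes four to six leftover stool samples per group as donors for transplantation into mice, with no drug-exposure condition.
- **Analysis.** Section 2.5 lists MaAsLin, random forest and other methods, but no covariates and no sensitivity analysis for medication.

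**The concern.** The drug criterion lists treatments that can alter the flora, yet its qualifiers leave out some that act on the gut most directly. An antibiotic that stays in the bowel need not count as systemic. A probiotic puts bacteria into the stool because they were swallowed. A PPI being taken on the day of sampling passes if the course is not regarded as chronic.

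If such use differs between groups, a taxon that the product supplies or suppresses will differ too and can be taken for a marker of disease. Neither the entry rules nor the analysis plan controls this. The donor samples raise a separate issue that does not depend on unequal use: with so few donors per group, one exposed donor is a sizeable share of what the mice receive.

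**Working it through.** The documents give no figure for drug use or drug effect, so no plan figure can be reproduced. The check has a reading step and three illustrations.

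**1. Does another provision close the gap?**
- Criterion (1) looks back one month and criterion (5) three. A non-systemic antibiotic given in the second or third month before enrolment, for an infection since resolved, is caught by neither.
- Criterion (4) depends on a gastrointestinal disease history. A probiotic or PPI taken without such a history passes.
- The drug-history item cannot, as worded, guarantee that a product and its date are recorded.
- MaAsLin can take covariates, but section 2.5 names none.

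The gap is narrowed, not closed.

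**2. How large could the effect on a group comparison be?**

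From the documents: 720 subjects in four groups (section 2.1) and alpha 0.05 (section 2.5). Assumed: equal split, 720/4 = 180 per group; one taxon; no true disease effect; no adjustment; and the values for use and drug effect.

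Spurious difference d = (difference in proportion using) × (drug effect in SD). With unit variance, se = √(2/180) = 0.105. Two-sided rejection probability = Φ(d/se − 1.96) + Φ(−d/se − 1.96).

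| Excess use in patients | Effect 0.3 SD | 0.5 SD | 0.8 SD |
|---|---|---|---|
| 0 points | 0.050 | 0.050 | 0.050 |
| 5 points | 0.052 | 0.056 | 0.067 |
| 10 points | 0.059 | 0.076 | 0.118 |
| 20 points | 0.088 | 0.158 | 0.329 |
| 30 points | 0.137 | 0.296 | 0.624 |

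For a 1 SD effect and 2% use in healthy controls, the mixing of users and non-users is added to the variance, 1 + p(1 − p):
- 20% use in patients: d = 0.18; se = √((1.16 + 1.0196)/180) = 0.110; z = 1.64; rejection probability 0.37.
- 30% use in patients: d = 0.28; se = √((1.21 + 1.0196)/180) = 0.111; z = 2.52; rejection probability 0.71.

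**3. How likely is an exposed donor?**

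If a proportion p of a group is exposed and k donors are drawn at random, P(at least one exposed) = 1 − (1 − p)^k.
- p = 10%: 1 − 0.9⁴ = 34% for four donors; 1 − 0.9⁶ = 47% for six.
- p = 20%: 1 − 0.8⁴ = 59% for four; 1 − 0.8⁶ = 74% for six.

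One exposed donor is 1/6 to 1/4 (17% to 25%) of that group's donors.

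**4. What would exclusion at entry cost?**

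With 3 × 180 = 540 patients wanted, the number to screen is 540/(1 − p).
- p = 5%: 540/0.95 = 568, about 28 extra.
- p = 20%: 540/0.80 = 675, 135 extra.
- p = 30%: 540/0.70 = 771, about 231 extra.

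**The case against.** A reader might infer that patients do use these products more than healthy controls, and hence that the marker findings will be biased. The documents do not support that, because they give no usage data for any group. Recruiting patients from hospital departments and controls from the public makes unequal use plausible, no more.

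A reader might also infer that a site would readily enrol a patient on a bowel antibiotic plus a probiotic. That overlooks criteria (1) and (4), and criterion (3) on other unstable chronic disease, which remove many people with a reason to take these products. These objections stand. They limit the size of the problem but do not remove it, since none of those criteria concerns a drug.

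The contrast between hospital and public recruitment bears on comparisons with healthy controls. DKD, T2DM and CKD patients all come from the same two departments, so it gives no reason to expect unequal use among them, and those comparisons are the ones that would show a marker to be specific to DKD. This also stands.

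Finally, which drugs bar entry is the investigators' choice, and changing the rule in an ongoing study produces two differently selected cohorts. Nor can heavy use be combined with a claim that few would be screened out: the use rates that make the bias serious are those that make exclusion costly. This argues for putting recording and analysis first, with a change to entry as an option.

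**Conclusion.** The point holds in a limited form. As worded, the plan lets three flora-altering exposures into the main comparison and the donor pools in every group, and provides no analytic control for them. These products are not expressly permitted; the text simply does not exclude them.

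The consequence cannot be fixed from the documents. Assuming 180 per group, one taxon, no disease effect and no adjustment, the false-positive probability runs from about 0.05 (5-point gap, 0.3 SD), which is negligible, to about 0.7 (28-point gap, 1 SD), which is serious. The upper end is an unfavourable case, not an expectation. Any confounding would fall mainly on patient-versus-healthy contrasts. The donor concern applies within each group, whether or not use is unequal.

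A change is worth making because the flora is the central measurement and the main remedy is cheap.

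**What to change.** 1. **Record exposure.** In all four groups, record any oral or systemic antibiotic, any probiotic and any PPI, by class and date, over the three months that criterion (5) already uses. For subjects already enrolled, complete this from existing records where possible and mark the rest as unknown.
2. **Pre-specify the analysis.** Enter exposure as a covariate in the MaAsLin model and rerun the whole marker analysis without exposed subjects. The rerun is needed because a MaAsLin covariate does not adjust the other listed methods, such as random forest.
3. **Screen donors.** Do not use exposed subjects' stool as transplant donor samples.
4. **Consider the entry rule.** For subjects still to be enrolled, the investigators should consider extending criterion (5) to these exposures, identically in all four groups.

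**Cost.** Steps 1 to 3 need slightly more data collection and some loss of precision in the rerun. For example, if 20% of a patient group of 180 were exposed, 144 would remain, and the standard error against 180 controls would rise from √(2/180) = 0.105 to √(1/144 + 1/180) = 0.112 SD, about 6%. Step 4 brings screen failures in proportion to actual use, as in part 4 of the working. No step changes or stops anyone's treatment.

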### 2.4 Study procedures

#### 2.4.1 Questionnaire to collect information

(1) General items: name, gender, age, BMI, education level, labor intensity, dietary preferences, etc;

(2) TCM symptoms, tongue and pulse;

(3) Clinical information: disease duration, other complications (e.g., diabetic peripheral neuropathy, diabetic retinopathy, diabetic cardiomyopathy, etc.), concomitant diseases (hypertension, coronary artery disease, hyperlipidemia, cerebrovascular disease, and hyperuricemia, etc.), past medical history, history of smoking, alcohol, family history, and history of drug use.

#### 2.4.2 Outcome Measures

Indicators of safety: Physical examination (including general condition, blood pressure, heart rate, heart rhythm, body temperature, respiratory rate, etc.) was

performed before taking the samples to assess the basic condition of the subjects.

**Primary Outcome Measures :** Urine Albumin-to-Creatinine Ratio(UACR), Estimated Glomerular Filtration Rate(eGFR),blood urea nitrogen(BUN), serum creatinine(Scr), fasting blood glucose(FBG), Glycosylated Hemoglobin, Type A1C(HbA1c), glucosylated serum protein(GSP) , etc. Test data were obtained from test results conducted within one month of enrollment for the purpose of evaluation.

**Secondary Outcome Measures:** 16S ribosomal DNA(16S rDNA) identification, metagenomic Next Generation Sequencing, Non-targeted and targeted Metabolomics technology detection , etc.

## 2.5 Data analysis

SPSS 26.0 will be applied for statistical analysis of clinical indicators. Data that exhibited a normal distribution were expressed as the mean  $\pm$  standard deviation(  $x \pm s$ ), and an independent samples t-test was employed for comparison between two groups. Data that did not conform to a normal distribution were expressed as the median and interquartile spacing [M(IQP)], and a Mann-Whitney rank-sum test (U test) was used for comparison between two groups. In the case of count data, these were expressed as frequencies or percentages. In the event of unordered categorical count data, comparisons between two groups were performed using either the four-cell table or the column table  $c^2$  test. The Pearson  $c^2$  test or Fisher's exact probability method was employed in accordance with the sample size and the size of the theoretical frequency. In the case of ordered categorical count data, comparisons between two groups were performed using the U test. A two-sided test was employed for the normality test and variance chi-square test, with an alpha level of 0.1. This resulted in the rejection of the original hypothesis, indicating that the data are not normally distributed or that there is no significant variance. For other significance tests, an alpha level of 0.05 was used, leading to the rejection of the original hypothesis and the conclusion that the difference is statistically significant.

An integrated correlation analysis will be performed using a variety of analytical techniques, including intestinal flora species diversity analysis, Spearman's correlation analysis, network analysis, Procrustes analysis, MaAsLin analysis, ERMANOVA analysis, random forest analysis of differential intestinal flora with differential metabolites between groups, and efficacy evaluation.

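### The variance-test rule in section 2.5 is stated backwards and leads to no choice of test; no unequal-variance test is named (minor)

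*Combined protocol and SAP*

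**What the plan says.** Section 2.5 (Data analysis) of the combined protocol and SAP sets these rules for the clinical indicators:

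- **Normal data:** "an independent samples t-test was employed for comparison between two groups". The form of the t-test, pooled or unequal-variance, is not given.
- **Non-normal data:** "a Mann-Whitney rank-sum test (U test) was used for comparison between two groups".
- **Preliminary tests:** "A two-sided test was employed for the normality test and variance chi-square test, with an alpha level of 0.1". Rejection is then explained as "indicating that the data are not normally distributed or that there is no significant variance".
- **Main comparisons:** "For other significance tests, an alpha level of 0.05 was used".

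On group sizes, section 2.1 says: "The total number of individuals proposed to be recruited in the four groups is 720". No split between the four groups (DKD, T2DM, CKD, healthy) is given, and no SDs appear anywhere.

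**The concern.** The null hypothesis of a homogeneity-of-variance test is that the variances are equal, so rejection is evidence that they differ. The plan attaches the opposite or an empty meaning to rejection. It also never says what the analyst does next: normality alone decides between the t-test and the Mann-Whitney test.

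SPSS, the software named in section 2.5, prints an equal-variance and an unequal-variance line for the independent-samples t-test. The analyst must report one of them, and the only sentence in the plan that bears on the choice points, if taken literally, to the equal-variance line when the variances differ.

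Unequal spread is plausible here. The groups are defined by diabetes and kidney disease, and section 2.4.2 lists glucose and renal measures as primary outcome measures. At stake is whether the stated 0.05 level is delivered for those comparisons. There is also an avoidable choice between two printed p-values after the data are seen.

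**Working it through.** The plan states no figure that depends on this rule, so there is nothing of its own to reproduce. The check has two parts.

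**1. The wording, half by half**

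| Preliminary test | Null hypothesis | What rejection means | What section 2.5 says rejection means | Action in section 2.5 |
|---|---|---|---|---|
| Normality | data are normal | data are not normal | data are not normal | Mann-Whitney instead of t-test |
| Variance | variances are equal | variances differ | no significant variance | none |

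**2. What follows if the pooled t-test is reported**

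Inputs from the documents: alpha 0.05 for the main comparisons (two-sided assumed; section 2.5 does not state it for these tests), alpha 0.1 for the variance test, total 720 in four groups. An equal split would be 720/4 = 180 per group.

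Assumptions, not in the documents: pairs of groups sized 180/180, 120/240 and 90/270; SD ratios from 1 to 3; normal data with equal means.

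Let group 1 have SD *r* and group 2 have SD 1. The pooled test estimates the variance of the mean difference as A = s²(1/n₁ + 1/n₂), with s² = [(n₁−1)r² + (n₂−1)]/(n₁+n₂−2). The true variance is B = r²/n₁ + 1/n₂. In large samples the type I error is 2[1 − Φ(1.96·√(A/B))].

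- **120/240, smaller group more variable, r = 2.** s² = (119×4 + 239)/358 = 1.997. A = 1.997 × 0.0125 = 0.02497. B = 4/120 + 1/240 = 0.0375. √(A/B) = 0.816. 1.96 × 0.816 = 1.599. Type I error = **0.110**.
- **240/120, larger group more variable, r = 2.** s² = (239×4 + 119)/358 = 3.003. A = 3.003 × 0.0125 = 0.03753. B = 4/240 + 1/120 = 0.025. √(A/B) = 1.225. 1.96 × 1.225 = 2.402. Type I error = **0.016**.
- **180/180, r = 2.** s² = 2.5. A = B = 0.02778. Type I error = **0.050**.

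Simulation with 40,000 data sets per setting (Monte Carlo standard error about 0.001 near 0.05):

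| n, more variable group | n, other group | Pooled, SD ratio 1.5 | Pooled, ratio 2 | Pooled, ratio 3 | Welch, ratio 2 |
|---|---|---|---|---|---|
| 180 | 180 | 0.050 | 0.050 | 0.055 | 0.050 |
| 120 | 240 | 0.085 | 0.108 | 0.137 | 0.051 |
| 240 | 120 | 0.026 | 0.017 | 0.011 | 0.050 |
| 90 | 270 | 0.109 | 0.151 | 0.201 | 0.052 |
| 270 | 90 | 0.019 | 0.008 | 0.003 | 0.051 |

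The 0.055 at 180/180 is simulation noise: the formula gives 0.050, and a repeat with 80,000 data sets gave 0.051.

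A mean-centred Levene test at 0.10 rejected in more than 99% of data sets at every SD ratio of 1.5 or above. Two things follow. A literally reversed rule (pooled on rejection, Welch otherwise) has the same error as always pooling. The rule the right way round (Welch on rejection) matches Welch throughout, at 0.049 to 0.054 across all settings.

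**Price of Welch when variances are equal.** At 180/180 with equal sample variances the two tests coincide. At 120/240 the Welch degrees of freedom are 0.0125² / [(1/120)²/119 + (1/240)²/239] ≈ 238 against 358 for the pooled test. The critical value moves from 1.967 to 1.970.

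**The case against.** The strongest reply is that this is a language slip with little consequence. The normality half is correct, and the variance half sits in the same negative frame, so the intended meaning was probably that the variances are not homogeneous. Neighbouring terms in section 2.5 are garbled too. A planned variance test most naturally serves to choose between the two SPSS lines. This is a fair inference, but it does not fill the gap: the choice is still unwritten and no unequal-variance test is named.

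A reader might infer that the plan keeps the pooled t-test exactly where its assumption fails. The documents do not support that. Section 2.5 never specifies the pooled form and ties no test to the variance result. Pooling follows only if the sentence is applied literally or the equal-variance line is reported.

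Three further limits stand:

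- With 180 per group the distortion is negligible. Larger figures need unequal sizes and unequal SDs together, and the documents give neither.
- Variables that fail the normality test go to Mann-Whitney, so strongly skewed measures are largely outside the problem. For indicators that define the groups, equal means are not a realistic null when diseased and healthy subjects are compared, so type I error matters less there.
- The flora and metabolite markers, which section 2.2 names as the primary outcome, are analysed by the separate methods in the second paragraph of section 2.5. That section plans no confidence intervals and no four-group test, so nothing can be claimed about either.

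**Conclusion.** The point holds as a defect in a working analysis rule, of minor severity. The reversed reading of the variance test and the absence of any follow-on test are both plain in section 2.5.

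The numerical effect is conditional. If the pooled result is reported, and under the assumed SD ratio of 2, the nominal 0.05 becomes about 0.11 at 120/240 with the smaller group more variable and about 0.017 with the larger group more variable. It stays at about 0.05 at 180/180. Because section 2.1 fixes only the total of 720, the balanced case cannot be taken for granted, but nothing in the documents points to a particular imbalance either. Only two-group comparisons of clinical indicators that pass the normality test are affected.

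**What to change.** In section 2.5, do one of the following:

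1. Delete the variance pre-test and its interpretation, and state that two-group comparisons of approximately normal clinical indicators use Welch's t-test (the unequal-variance line in SPSS).
2. Keep the pre-test, state that rejection means unequal variances, and state that Welch's t-test is then used.

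The two are equivalent in type I error in the settings checked; the first is simpler. Either changes one sentence, needs no new data or software, and loses negligible power if the variances are in fact equal.

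### Section 2.5 names Spearman correlation and network analysis for sequencing-derived flora with no compositional handling; on relative abundances this can create false flora-flora edges and spread a metabolite's true link to unrelated taxa.

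*Combined protocol and SAP*

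**What the plan says.** Section 2.4.2 lists the omics measurements as "16S ribosomal DNA(16S rDNA) identification, metagenomic Next Generation Sequencing, Non-targeted and targeted Metabolomics technology detection". It describes no total-load measurement, spike-in or other route to absolute abundance.

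Section 2.2 makes it the secondary outcome to "analyze the interaction between intestinal flora and intestinal-derived metabolites in the disease process of DKD".

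Section 2.5 gives the omics analysis in one sentence. After flora diversity it lists "Spearman's correlation analysis, network analysis", then Procrustes, MaAsLin and ERMANOVA, followed by "random forest analysis of differential intestinal flora with differential metabolites between groups". It does not say whether counts, proportions or log-ratios enter the correlations, how zeros are treated, which network algorithm is used, or what makes an edge. The only general test level is in the clinical-indicator paragraph: "For other significance tests, an alpha level of 0.05 was used". No multiplicity rule appears. Two-sidedness is stated only for the normality and variance tests ("A two-sided test was employed for the normality test and variance chi-square test, with an alpha level of 0.1").

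Section 2.1 gives a total of 720 subjects in four groups, with no split.

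**The concern.** Without absolute quantification, sequencing fixes abundances only relative to each other. Within a subject, a rise in one taxon's share lowers the shares of the others. A rank correlation between two shares is therefore not a test of association between the two taxa's absolute abundances, and it can be non-zero when the taxa are unrelated.

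For flora-metabolite pairs the route is narrower, because the metabolite lies outside the composition. If it truly tracks a dominant taxon, the other taxa's shares move against that taxon, so the metabolite appears linked to them as well.

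At stake is the secondary outcome. An edge list that mixes real links with closure artefacts cannot be read as interaction. Covariate adjustment does not address closure. Nor does a larger sample: on shares the null hypothesis of no association is false, so more subjects make the artefact easier to detect.

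**Working it through.** **Inputs from the documents.** Level 0.05 (2.5) and 720 subjects in four groups (2.1). No effect size, standard deviation, power or allocation supports the 720, so there is no plan figure to reproduce.

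**Assumptions.** Equal groups, 720 / 4 = 180; two-sided tests; 20, 100 or 300 taxa; 50 metabolites. Absolute abundances are independent log-normal, so every taxon-taxon edge is false. *Even* means SD 1 for the log means and SD 1 within taxon; *uneven* means 2 and 1.5. There are 8 replicates per setting, no group differences and no zeros.

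**Formulas.**
- Closure: share r_ij = a_ij / Σ_k a_ik.
- CLR: c_ij = log r_ij − mean_k(log r_ik).
- Spearman test: t = r√((n−2)/(1−r²)) on n−2 df.
- Benjamini-Hochberg (BH) at 5%: reject up to the largest k with p_(k) ≤ 0.05k/m.

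In the flora-metabolite columns, each metabolite correlates about 0.5 with the most abundant taxon only, and hits on the other taxa count as false.

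**Results: % of null pairs flagged**

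| n | Taxa | Community | Flora-flora, shares | same, BH | same, CLR | Flora-metabolite, shares | same, CLR |
|---|---|---|---|---|---|---|---|
| 180 | 20 | even | 18.2 | 5.4 | 10.9 | 22.1 | 6.4 |
| 180 | 20 | uneven | 43.0 | 30.5 | 10.5 | 34.5 | 6.3 |
| 180 | 100 | even | 6.4 | 0.0 | 5.4 | 7.5 | 4.9 |
| 180 | 100 | uneven | 16.4 | 0.5 | 5.3 | 12.1 | 4.7 |
| 180 | 300 | even | 5.1 | 0.0 | 5.0 | 5.4 | 5.1 |
| 180 | 300 | uneven | 14.0 | 1.3 | 5.0 | 14.2 | 5.0 |
| 720 | 20 | even | 44.5 | 29.8 | 27.0 | 62.7 | 10.2 |
| 720 | 20 | uneven | 85.3 | 84.7 | 27.3 | 91.1 | 10.1 |
| 720 | 100 | even | 12.6 | 2.3 | 5.8 | 23.8 | 4.9 |
| 720 | 100 | uneven | 63.2 | 53.7 | 5.9 | 47.4 | 5.5 |
| 720 | 300 | even | 5.7 | 0.0 | 5.1 | 7.8 | 5.0 |
| 720 | 300 | uneven | 42.3 | 25.3 | 5.1 | 39.4 | 5.1 |

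On unclosed abundances, both kinds of pair were flagged about 5-6% of the time. Metabolites independent of all flora were flagged on shares 4.6-5.4% of the time in every setting.

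**Closed-form check of the CLR columns.** For p independent taxa of equal variance, the CLR correlation of two taxa is −1/(p−1). With p = 20 this is −0.0526, or (6/π)·asin(−0.0526/2) = −0.0503 on the rank scale.
- n = 180: 0.0503 × √179 = 0.673; P(Z > 1.96 − 0.673) + P(Z > 1.96 + 0.673) = 10.3%.
- n = 720: 0.0503 × √719 = 1.348, which gives 27.1% in the same way.

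These agree with the simulated 10.5-10.9% and 27.0-27.3%. The residual excess is thus a property of CLR with few taxa, not simulation noise.

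**Sensitivity to the community.** With 50 taxa at n = 180, mean-log SD 1.5, within-taxon SD 1 and a dominant taxon holding 17%, 23% or 31% of reads, false flora-flora edges were 22-38% and false flora-metabolite edges 20%, 31% and 44%. CLR gave 6% and 5%. With the same spreads, 300 taxa and no raised dominant taxon, the rates on shares fell to 7% and 10%.

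**Sensitivity to zeros.** With simulated reads, 300 taxa, 44% zeros, a 10% prevalence filter and a 0.5 pseudocount, CLR flagged 21% of null taxon pairs (shares 18%) and 15% of unrelated taxon-metabolite pairs (shares 20%). With 26% zeros, CLR flagged 8% and 6%. In a separate sparse simulation, CLR gave 8-11% with a 10% filter and 5-6% with a 50% filter.

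**The case against.** The strongest reply is that section 2.5 is a list of technique names. It does not say that untransformed shares will be used, and its unnamed network analysis could be a compositional one. This stands: a reader might infer that the plan prescribes a wrong analysis, but it leaves the step open. What remains is that it permits the faulty analysis on the usual sequencing output and lets the scale be chosen after the data are seen.

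A reader might also infer that flora-metabolite edges are inflated in general. They are not: metabolites unrelated to the flora kept their level. The spread needs a metabolite that truly tracks a dominant taxon, and the documents do not say how common such metabolites are. They are, however, what a study of gut-derived metabolites is looking for.

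The size depends on community features that the documents do not give. With 300 even taxa the excess is near zero at n=180 and at most about 3 points at n=720 (7.8% against 5%). BH also works in some settings, leaving 2.3% and 0% of null flora-flora pairs flagged at n=720 with 100 and 300 even taxa.

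Finally, MaAsLin and random forest are listed too, and nothing says that markers are chosen from Spearman edges. That is correct, so the point rests on the interaction outcome. Equally, nothing says that those methods correct or confirm the edges.

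**Conclusion.** The concern holds in conditional form. The plan names correlation and network methods for sequencing-derived flora without compositional handling or absolute quantification. If they are run on relative abundances, flora-flora edges, and flora-metabolite edges that share a dominant taxon, cannot be told from closure artefacts.

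Under the assumed communities, false flora-flora edges at n=180 range from about 5% to 43%. At n=720 the range is 6% to 85%, and BH leaves up to 85% of null pairs flagged with few, uneven taxa. All inputs except 720 and 0.05 are assumptions. The pooled runs show the effect of sample size only, since no group differences were simulated.

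The documents do not support the reading that the reported links would be only artefacts, or that many false edges are certain. Real associations would be mixed in, and the excess depends on the number of taxa, their evenness, the sample size and the true signal. Nor should the benefit of CLR be quoted as a fixed 5%.

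**What to change.** In section 2.5, state that:
- flora data are prevalence-filtered, zero-replaced by a named rule and CLR-transformed before Spearman correlation with metabolites;
- taxon-taxon networks use a named compositional method, for example SparCC or SPIEC-EASI;
- the untransformed result, and one alternative zero replacement or prevalence filter, are reported as sensitivity analyses.

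The cost is a short addition to 2.5, standard software and the extra sensitivity runs. No new samples or measurements are needed, and section 2.1 describes the study as ongoing. The downside is that CLR results depend on zero handling and keep some excess false edges with few taxa or very sparse data. For that reason the taxon-taxon network needs its own method and the alternative zero or filter run should be reported.
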